6.1 Trial treatments administered

Name	mFOLFIRINOX	BNT321
Trial treatment type	Chemotherapy	Monoclonal antibody
Dosage form	NA	BNT321 is provided as a single-use glass vial containing 8.0 mL of sterile solution at 10 mg/mL in a buffer at pH 6.0, containing 25 mM histidine, 150 mM sucrose, 55 mM sodium chloride, and 0.02% polysorbate 80.
Unit dose strength(s)	 Oxaliplatin: 85 mg/m² Leucovorin: 400 mg/m² Irinotecan: 150 mg/m² 5-FU: 2400 mg/m²* 	0.5 CCI mg/kg based on cohort
Dosage regimen	mFOLFIRINOX will be administered on the first day of each 14-day cycle (i.e., C1D1, C2D1, C3D1, and so on for a total of 12 cycles) using the following dose and schedule for each agent: • Oxaliplatin: Day 1 • Leucovorin: Day 1 • Irinotecan: Day 1 (starting 30 minutes after leucovorin) • 5-FU: Day 1	BNT321 will be incorporated into the mFOLFIRINOX regimen starting from the second cycle and after the completion of the 5-FU infusion (e.g., initially on C2D3).
Diluent	mFOLFIRINOX is prepared and administered according to institutional standards, in compliance with the package insert for each drug	Prior to infusion, BNT321 is diluted in normal saline to obtain a final concentration of less than 5 mg/mL

BioNTech SE Confidential Page 55 of 127 Version: 2.0 Date: 22 JAN 2024

Name	mFOLFIRINOX	BNT321
Route of administration	 Oxaliplatin: IV over 2 hours Leucovorin: IV over 2 hours Irinotecan: IV over 90 minutes 5-FU: Continuous IV infusion over 46 hours, following oxaliplatin, leucovorin, and irinotecan 	IV infusion for 2 hours
Sourcing	See the Pharmacy Manual	See the Pharmacy Manual
Packaging and labeling	For details see the Pharmacy Manual	For details see the Pharmacy Manual

^{*} Reduced 5-FU dose may be implemented for patients with DPD deficiency, per the discretion of the treating physician. Abbreviations: 5-FU = 5-fluorouracil; CnDn = cycle number day number; DPD = dihydropyrimidine dehydrogenase; IV = intravenous; NA = not applicable.

6.2 Rationale for the trial treatment (dose, route, frequency)

Modified FOLFIRINOX + BNT321 combination therapy has been evaluated as first and second line treatment for advanced PDAC in the BioNTech trial MV-0715-CP-001.01.

More than 60 cycles have been administered over a BNT321 dose range of CCI IV on a Q2W schedule. The BNT321 combination MTD is CCI IV Q2W in the metastatic setting and this is the highest prespecified dose cohort for the Phase I part of this trial adjuvant therapy. Additional BNT321 doses may be considered following comprehensive review of safety data and approval by an SRC that will be utilized for BNT321-02 Phase I. Extended course BNT321 monotherapy (Weeks 24 to 48) will be evaluated following the initial 12 cycles with combination chemotherapy. For Phase II patients randomized to BNT321 treatment, this 48-week regimen will be implemented following safety and RP2D determination in Phase I.

6.3 Dosing and administration

mFOLFIRINOX regimen

mFOLFIRINOX will be administered intravenously on the first day of the 14-day treatment cycle (i.e., on Day 1 of each cycle) using the following dose and schedule for each agent:

- Oxaliplatin, IV over 2 hours, 85 mg/m²
- Leucovorin, IV over 2 hours, 400 mg/m²
- Irinotecan, IV over 90 minutes, 150 mg/m² (starting 30 minutes after leucovorin)
- 5-FU, continuous IV infusion over 46 hours, 2400 mg/m², following oxaliplatin, leucovorin, and irinotecan

Modifications to the above dose and schedule for mFOLFIRINOX in response to toxicity considered secondary to mFOLFIRINOX will be made in accordance with Section 6.3.1.2 where specified, or otherwise with institutional SoC.

Page 56 of 127 Version: 2.0 Date: 22 JAN 2024

For BNT321 preparation, use of a patient's weight from the prior cycle is permitted. For patients who weigh more than 100 kg (220 pounds), the BNT321 administered dose should be calculated based on an adjusted weight of 100 kg.

The first dose of BNT321 for each patient will be administered as an IV infusion over at least 120 minutes. In patients who tolerate an initial infusion without difficulty, subsequent infusions may be reduced by 30 minutes to a minimum infusion duration of 60 minutes (i.e., a 120-minute infusion during the first infusion, a 90-minute infusion during the second infusion, a 60-minute infusion during the third and subsequent infusions). The BNT321 infusion duration should never be less than 60 minutes. Post-treatment monitoring period should be according to institutional guidelines.

Pre- and postmedications are defined in Section 6.9.3 and 6.9.2.

Patients with IRR should be treated according to Section 6.3.4.

Timing of BNT321 in relation to mFOLFIRINOX

BNT321 will be incorporated into the mFOLFIRINOX regimen from the second cycle onwards starting after the completion of the 5-FU infusion (i.e., initially on C2D3) and then every 2 weeks thereafter (i.e., Day 3 each cycle). In situations where the administration of mFOLFIRINOX is delayed or modified, any adjustment to the administration of BNT321 will be made in consultation with the Medical Monitor.

Patients in Phase I part of the trial, who have completed at least 8 weeks on trial (i.e., have completed the first four cycles), will have the option of receiving BNT321 earlier during each treatment course (e.g., on Day 1 of each cycle rather than Day 3). For all subsequent cycles, these patients are not required to come to the clinic on Day 3 of each cycle. Assessments called for on Day 3 will be moved to Day 1. In these patients, BNT321 should be administered after completion of irinotecan and prior to the start of the 5-FU infusion. Cycle Day 1 administration of BNT321 may be utilized for the Phase II part of the trial, following review of Phase I safety data and alignment with the SRC.

The Medical Monitor must be notified prior to implementing the modified assessment schedule for patients in Phase I, who have completed 8 weeks on trial and appear appropriate for consolidation of their treatment schedule.

6.3.1 Dose modifications

The SRC may request reduction of the planned dose and/or increase the interval between doses.

6.3.1.1 BNT321 dose delay or reduction (for BNT321-related events)

Prior to administration of all subsequent doses of BNT321, any clinically significant, BNT321 related, toxicity resulting from prior BNT321 administration must return to ≤ Grade 1 or baseline.

In the event that the administration of BNT321 was delayed for second incidence of Grade 2 or first incidence of Grade ≥3 BNT321-related toxicity, the patient may receive

Page 57 of 127 Version: 2.0 Date: 22 JAN 2024

subsequent administrations of BNT321 at a dose no more than 50% of the current dose. See Table 8 for specific dose modification guidelines for liver function tests (LFTs).

In the event that a clinically significant BNT321-related toxicity necessitates a delay of more than 14 consecutive days, the patient may be removed from trial treatment phase.

Re-escalation of BNT321 dose is not allowed for patients that previously have been dose reduced.

First occurrence of BNT321 related AE Grade ≥3 fulfilling DLT criteria:

- As a first measure, administration of BNT321 needs to be held.
- Investigator must contact the sponsor to discuss whether the patient should be withdrawn from BNT321 treatment or if the next dose should be delayed.
- Administration of BNT321 can be delayed for up to 14 days unless otherwise approved by the sponsor Medical Monitor. If the intensity of AEs resolves to Grade ≤1 within this period, retreatment may be considered under the following:
 - BNT321 should be administered at a dose of no more than 50% and after discussion with sponsor.

Second occurrence of an identical AE Grade ≥3 after re-exposure to BNT321:

- If retreatment leads to an identical AE with same intensity, the next administration of BNT321 should be stopped.
- Retreatment may only be considered on a case-by-case basis after review by the SRC.
- BNT321 must be permanently discontinued if the patient experiences an AE fulfilling the DLT criteria (after the DLT period has ended for the dose escalation) that fails to resolve to Grade ≤1 within 14 d after the planned dosing date, unless otherwise approved by the sponsor Medical Monitor.

Re-escalation of BNT321 dose is not allowed for patients that previously have been dose reduced.

The investigators are encouraged to contact sponsor in case of any safety concern that requires additional discussion or clarification.

BioNTech SE Confidential Page 58 of 127 Version: 2.0 Date: 22 JAN 2024

Table 8: BNT321 dose modifications: elevated bilirubin and/or transaminases

	Cycle delay	BNT321 Dose reduction/modification
Grade 1 bilirubin, ALT, or AST	No delay	None
Grade 2 bilirubin alone	Delay treatment until recovery Grade <1 (14 days maximum)	1st episode: 50%-100% redose If no recovery to Grade ≤1 in this time frame discontinue BNT321 and DLT should be reported per Section 6.3.2. 2nd episode: reduce dose to 50% 3rd episode: discontinue
Bilirubin >2 x ULN and ALT or AST >3 x ULN	Evaluate for Hy's criteria see liver safety evaluation per Section 10.6	If meets Hy's law and deemed to be related to BNT321 discontinue and do not redose. If determined to be unrelated to BNT321 restart at 50–100% dose, following recovery to Grade ≤1.
Grade 2 bilirubin and Grade <2 ALT/AST (not meeting Hy's law criteria per Section 10.6)	Delay treatment until recovery Grade <1 (14 days maximum)	1 st episode: 1 st episode: 50%–100% redose If no recovery to Grade ≤1 in this time frame discontinue BNT321 and DLT should be reported per Section 6.3.2. 2 nd episode: reduce dose to 50% 3 rd episode: discontinue
Grade 2 bilirubin and Grade 3 AST or ALT (not meeting Hy's criteria per Section 10.6)	Delay treatment until recovery Grade ≤ 1 (14 days maximum)	1 st episode: If recovery to Grade ≤1 within 14 days dose reduction by 50%. If no recovery to Grade ≤1 within this time frame discontinue BNT321 and report DLT per Section 6.3.2. 2 nd episode: discontinue BNT321
Grade 2 ALT or AST with normal bilirubin	Delay treatment until recovery Grade < 1 (14 days maximum)	1 st episode: 50%-100% redose If no recovery to Grade ≤1 in this time frame discontinue BNT321 2 nd episode: reduce dose to 50% 3 rd episode: discontinue
Grade 3 ALT or AST with normal bilirubin	Delay treatment until recovery Grade <1 (14 days maximum)	1 st episode: If recovery to Grade ≤1 within 14 days dose reduction by 50% If no recovery to Grade ≤1 within this time frame discontinue BNT321 and report DLT per Section 6.3.2. 2 nd episode: discontinue BNT321
Grade 3 bilirubin	Delay treatment until recovery Grade ≤ 1 1 (14 days maximum)	1 st episode: If recovery within 14 days dose reduction by 50%; If no recovery to Grade ≤1 within this time period discontinue BNT321 and report DLT per Section 6.3.2. 2 nd episode: discontinue BNT321

Page 59 of 127 Version: 2.0 Date: 22 JAN 2024

	Cycle delay	BNT321 Dose reduction/modification
Any event of Grade 4 ALT, AST, or bilirubin	Discontinue treatment	Discontinue BNT321 and report any related event as DLT per Section 6.3.2.

Abbreviations: ALT = alanine aminotransferase, ALT = alanine aminotransferase, DLT = dose-limiting toxicity, ULN = upper limit of normal.

For total bilirubin elevation dose modifications for irinotecan may be also indicated see Section 6.3.1.2.

For AEs occurring in combination part of trial (mFOLFIRINOX + BNT321) which are considered clearly not related to BNT321 but related to the mFOLFIRINOX and require delay or discontinuation of the mFOLFIRINOX regimen, continuation of BNT321 administration as monotherapy is permitted after the AE has resolved to Grade ≤ 1 or baseline.

6.3.1.2 mFOLFIRINOX dose delay or reduction

In case a dose reduction is necessary, the reduced dosage will be maintained until the end of treatment.

In case of recurrent Grade 4 toxicity despite dose reduction, the investigator and the sponsor may discuss the possibility of stopping the treatment.

Table 9: Hematological toxicity based on Day 1 ANC and platelet count

	Cycle delay	Dose reduction		
		Irinotecan	Oxaliplatin	5-FU/leucovorin
Neutrophils <1.5 x 10 ⁹ /L	Delay treatment until	1 st episode: dose reduction to 120 mg/m ²	1 st episode: no dose reduction	1 st episode: no dose reduction
	neutrophils are ≥1.5 x 10 ⁹ /L	2 nd episode: maintain dose at 120 mg/m ²	2 nd episode: reduce dose to 60 mg/m ²	2 nd episode: no dose reduction
	and resume cycle with G-CSF*	3 rd episode: discuss treatment stop or maintain only LV/5-FU	3 rd episode: discuss treatment stop or maintain only LV/5-FU	
Platelets <100 x 10 ⁹ /L	Delay treatment until recovery	1 st episode: no reduction in dose	1 st episode: reduce dose to 60 mg/m ²	1 st episode: no dose reduction
	(platelets ≥100 x 10 ⁹ /L)	2 nd episode: reduce dose to 120 mg/m ²	2 nd episode: maintain dose at 60 mg/m²	2 nd episode: reduce the dose of IV continuous infusion
		3 rd episode: discuss withholding irinotecan*	3 rd episode: discuss withholding oxaliplatin*	by 25%
				3 rd episode: discuss withholding 5-FU

Page 60 of 127 Version: 2.0 Date: 22 JAN 2024

*Granulocyte colony stimulating factor and other hematopoietic growth factors may be used in the management of acute toxicity (such as febrile neutropenia) or prophylactically, when clinically indicated at the investigator's discretion. Blood cell transfusion (RBC or platelet) is allowed if clinically indicated. See Section 6.9.2 for more information.

Abbreviations: CBC = complete blood count; G-CSF = granulocyte colony stimulating factor; IV = intravenous; 5-FU =

5-fluorouracil; RBC = red blood cell.

Table 10: Hematological toxicity during the inter-cycle interval (nadir) with mFOLFIRINOX

Events	Dose reduction
Febrile neutropenia isolated Grade 4 neutropenia >7 days Infection with	1st episode: reduce irinotecan dose to 120 mg/m² plus G-CSF
concomitant Grade 3 to 4 neutropenia	2 nd episode: in addition, reduce oxaliplatin dose to 60 mg/m ²
	3 rd episode: discuss growth factor or further treatment reduction, maintain only LV/5-FU if necessary
Thrombocytopenia, Grade 3 to 4	1st episode: reduce the dose of oxaliplatin to 60 mg/m²
	2 nd episode: in addition, reduce the irinotecan dose to 120 mg/m² and reduce 5-FU IV continuous by 25%
	3 rd episode: stop oxaliplatin and irinotecan, discuss withholding LV/5-FU

Abbreviations: G-CSF = granulocyte colony stimulating factor; IV = intravenous; LV/5-FU = continuous infusion of 5-fluorouracil and leucovorin.

Table 11: Gastrointestinal toxicities with mFOLFIRINOX

Events	Dose reduction
Isolated Grade 3 to 4 diarrhea OR diarrhea + fever AND/OR	1 st episode: reduce irinotecan to 120 mg/m ²
Grade 3 to 4 neutropenia	2 nd episode: reduce oxaliplatin to 60 mg/m ² and reduce 5-FU continuous by 25%
	3 rd episode: stop irinotecan
Recurrent diarrhea (>48 h) despite high doses of loperamide*	Irinotecan, oxaliplatin and 5-FU should be delayed by one week until Grade 1 or less, and redose at same level

^{*}In no instance should loperamide be administered for more than 48 consecutive hours.

In case of occurrence of gastrointestinal ulceration, hemorrhagic or not, treatment with 5-fluorouracil should be stopped until disappearance of symptoms.

Abbreviation: 5-FU = 5-fluorouracil.

Supportive and prophylactic management per institutional guidelines and SmPCs for mFOLFIRINOX individual drugs.

Mucositis

These toxicities are caused by 5-FU. If Grade 3 to 4 toxicity occurs, 5-FU IV continuous infusion will be reduced by 25% for the remaining courses. Supportive care and prophylactic measures per institutional guidelines.

Page 61 of 127 Version: 2.0 Date: 22 JAN 2024

Cardiac toxicity

In case of angina pectoris with clinically significant ECG changes or myocardial infarction, 5-FU treatment shall be stopped. The reintroduction of 5-FU is not permitted.

Peripheral neuropathy

The dose of oxaliplatin can be adapted according to Table 12.

Table 12: Recommended dose modifications for oxaliplatin

Toxicity	≤7 days	>7 days and <14 days	Persisting between cycles
Asymptomatic or paresthesia/dysesthesia without functional alteration (Grade 1)	No modification	No modification	No modification
Moderate symptoms; limiting instrumental activities of daily living (Grade 2)	No modification	No modification	65 mg/m ²
Severe symptoms; limiting self-care activities of daily living (Grade 3)	65 mg/m ²	65 mg/m ²	Stop
Life-threatening consequences: urgent intervention indicated	N/A	N/A	Stop
Acute laryngopharyngeal dysesthesia	Prolong infusion duration to 6 hours. Add (if not previously done) 1 g of calcium gluconate and 1 g of magnesium sulfate over 15 min before the oxaliplatin infusion. Action to be repeated after the oxaliplatin infusion.		

If oxaliplatin is stopped because of neurotoxicity, irinotecan and 5-FU should be continued.

Elevated bilirubin

If bilirubin increase is >1.5 ULN, it is preferable to postpone mFOLFIRINOX chemotherapy because irinotecan has biliary elimination. The presence of a tumor relapse or obstruction of biliary anastomosis must be checked. Indication of chemotherapy will be retained, if these two diagnoses are eliminated. However, it is preferable to stop irinotecan if bilirubin elevation is persistent.

Other toxicities

Other Grade 2 toxicities, except anemia and alopecia, may justify a dose reduction of 25%. If it is medically indicated, for instance, reduction of irinotecan to 120 mg/m² and/or oxaliplatin to 60 mg/m² and/or 5-FU decreased by 25% depending on the type of toxicity.

Page 62 of 127 Version: 2.0 Date: 22 JAN 2024

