6.3.2 Dose-limiting toxicity (DLT)

For all Phase I cohorts the DLT assessment period will encompass the treatment cycles of the first two consecutive BNT321 doses. Practically, this is 28 days within treatment Cycles 2 and 3.

To be considered a DLT, an AE must meet the following three criteria:

- Occurs during the DLT assessment period of BNT321.
- Is considered BNT321-related (i.e., definitely related or possibly related).
- Occurs in the presence of adequate supportive care (e.g., Grade 3 vomiting despite use of an appropriate anti-emetic regimen).

In addition, to be considered a DLT, an AE must meet at least one of the criteria listed below using CTCAE v5.0 criteria.

- Grade 4 hematologic toxicity (except for: Grade 4 thrombocytopenia without bleeding).
- Grade 3 or higher febrile neutropenia (i.e., ANC <1.0 × 10⁹ cells/L with a single temperature of >38.3°C [>100.9 F] or a sustained temperature of ≥38°C [≥100.4 F] for more than 1 h).
- Grade 3 thrombocytopenia associated with bleeding requiring platelet transfusion.
- Grade 3 microangiopathic hemolytic anemia.
- Grade 3 or higher non-hematologic toxicity (except for: Grade 3 peripheral neuropathy <14 days, Grade 3 fatigue for <7 days, Grade 3 AST or ALT for <14 days, Grade 3 total bilirubin for <72 hrs and not associated with Grade 3 or higher AST or ALT).
- Total bilirubin ≥2 x ULN for >14 consecutive days.
- Grade 2 total bilirubin in association with a Grade 3 or higher ALT or AST (also requires discontinuation of BNT321).
- · Grade 2 or higher hemolysis.
- Delay for >14 consecutive days in administration of the second cycle of BNT321 secondary to liver toxicity (i.e., persistent elevations for this time period of serum transaminase and/or bilirubin).

Patients who will not be able to fulfill the criteria for the DLT assessment will be replaced (this only applies to patients who do not experience a DLT). Replaced patients can continue with BNT321 treatment and follow the same trial procedures except for DLT assessment until they meet the protocol-defined treatment discontinuation criteria.

Page 63 of 127 Version: 2.0 Date: 22 JAN 2024

The SRC will have the option of declaring other toxicities not listed above as DLT. These include sequalae (e.g., encephalopathy) considered related to AST or ALT elevations even if such elevations do not meet the Grade criteria stated above.

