10.6 Liver safety: Suggested actions and follow-up assessments

Patients with post-treatment transaminase elevations greater than three times ULN concurrent with total bilirubin >2 x ULN should be assessed for potential drug induced liver injury (DILI) per Hy's law criteria. Initial management includes withholding trial treatment according to specifications in Section 6.3.1.1 and 6.3.1.2. In such cases additional work up is warranted, including the following:

- Repeat transaminases and serum bilirubin tests two or three times weekly. Other
 laboratory tests to consider include albumin, CK, direct and indirect bilirubin, GGT,
 PT/INR, total bile acids, and alkaline phosphatase. The frequency of re-testing can
 decrease to once a week or less if abnormalities stabilize
- Obtain a more detailed history of symptoms and prior or concurrent diseases
- Obtain other history including review of family history, sexual history, travel history, history of contact with a jaundiced person, surgery, blood transfusion, history of liver or allergic disease, and potential occupational exposure to chemicals
- Assessment of history of concomitant drug use (including nonprescription medications, acetaminophen/paracetamol and herbal and dietary supplement preparations), alcohol use, recreational drug use, and special diets
- Other assessments may include testing for acute viral etiologies (hepatitis types A, B, C, D, and E; acute EBV or CMV infections), autoimmune or alcoholic hepatitis, NASH, hypoxic/ischemic hepatopathy, and biliary tract disease
- Evaluation for obstructive etiologies (ultrasound or other diagnostic imaging method)
- Consideration of gastroenterology or hepatology consultations

All cases meeting the laboratory criteria of AST/ALT and TBili elevation defined above should be considered potential DILI (Hy's law) cases if no other reason for the LFT abnormalities has been found.

Such potential DILI cases are to be reported as AESI, irrespective of availability of all the results of the investigations performed to determine etiology of the LFT abnormalities.

A potential DILI (Hy's law) case becomes a confirmed case only after all results of reasonable investigations have been received and have excluded an alternative etiology.

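### A BNT321-related Hy's law case stops BNT321 permanently under Table 8 but is not a listed DLT; below Grade 3 after the second dose, it counts as DLT-free unless the SRC decides otherwise

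*Combined protocol and SAP*

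**What the plan says.** The Hy's law row of Table 8 applies when bilirubin exceeds 2 × ULN and ALT or AST exceeds 3 × ULN. Its instruction is: "If meets Hy's law and deemed to be related to BNT321 discontinue and do not redose". If the case is judged unrelated, BNT321 may restart after recovery. The row does not mention a DLT. Section 10.6 uses the same laboratory pattern: "transaminase elevations greater than three times ULN concurrent with total bilirubin >2 x ULN should be assessed for potential drug induced liver injury (DILI". It sets no grade or duration floor, and adds: "A potential DILI (Hy's law) case becomes a confirmed case only after all results of reasonable investigations have been received".

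Section 6.3.2 sets the relatedness standard for a DLT ("Is considered BNT321-related (i.e., definitely related or possibly related") and then lists the qualifying toxicities. Its combined liver criterion is "Grade 2 total bilirubin in association with a Grade 3 or higher ALT or AST (also requires discontinuation of BNT321". Hy's law does not appear in the list. After the list comes a discretionary route: "The SRC will have the option of declaring other toxicities not listed above as DLT".

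Section 9.4 treats a patient without a DLT as evaluable if at least 80% of the planned BNT321 dose was given and the whole assessment period was followed. Section 4.1.5 replaces non-evaluable patients. It opens the next dose at 0 of 3 or at most 1 of 6, and declares the MTD exceeded at two or more DLTs.

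**The concern.** The protocol judges a related Hy's law case too dangerous to redose, yet the rule that decides whether a dose is tolerable has no line for it. Six of the nine Table 8 rows carry an instruction to report a DLT. The only other row that stops BNT321 at first occurrence with no route back is Grade 4, and it says: "Discontinue BNT321 and report any related event as DLT per Section 6.3.2". The silence of the Hy's law row therefore looks like an omission.

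At stake is the Phase I count. A patient withdrawn for drug-induced liver injury could be recorded as having tolerated the dose. Liver toxicity is the known dose-limiting signal: Section 2.3.2 describes three DLT patients among 15 given the combination in the metastatic setting, and all three DLTs were hepatic.

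**Working it through.** The plan gives no operating characteristics for the 3+3 part, so there is no figure to reproduce. The check has three steps.

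**1. Does any 6.3.2 criterion catch the case?** Take a related Hy's law case with ALT/AST above 3 × ULN and bilirubin above 2 × ULN, both below Grade 3, settling within 14 days.

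- Non-hematologic toxicity of Grade 3 or higher: not met.
- Grade 2 bilirubin with Grade 3 or higher ALT/AST: not met, because the transaminases are below Grade 3.
- Bilirubin of at least 2 × ULN for more than 14 days: not met.
- Second BNT321 cycle delayed by more than 14 days because of liver toxicity: this depends on timing. After dose 2 it cannot apply. After dose 1, a permanent stop means that dose 2 is never given, so the main clause may be met. However, the bullet explains the delay as elevations that last that long, and these did not.

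The protocol does not print the Grade 3 cut-offs. The gap exists if they lie above 3 × ULN for ALT/AST and above 2 × ULN for bilirubin. I assume more than 5 × ULN for ALT/AST from a normal baseline and more than 3 × ULN for bilirubin. If grading is relative to an abnormal baseline, the ALT/AST cut-off could reach 5 × 2.0 = 10 × ULN, because Section 5.2 admits values up to 2.0 × ULN.

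**2. How is the patient counted?** The assessment period covers two BNT321 doses.

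- Stopped after dose 2: 2/2 = 100% of the dose given. With full follow-up, the patient is evaluable and DLT-free.
- Stopped after dose 1: 1/2 = 50%, below 80%. If the delay criterion applies, this is a DLT. If not, the patient is non-evaluable and replaced.

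For a case counted DLT-free, a cohort with no other DLT reads 0 of 3 (open the next dose) instead of 1 of 3 (expand to six). A cohort of six with one listed DLT reads 1 of 6 (open the next dose) instead of 2 of 6 (MTD exceeded). Only the second change is decisive by itself, since 1 of 3 can still end at 1 of 6 and clear.

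**3. Illustration.** P(level clears) at DLT rate p is (1−p)³ + 3p(1−p)⁵. Let d be the rate of listed DLTs and h the rate of gap cases. The effective p is d if gap cases count as DLT-free, d/(1−h) if they are replaced, and d+h if they count as DLTs. Both rates are assumptions; d = 3/15 = 0.20 is the pooled figure from the earlier trial.

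At d = 0.20 the DLT-free value is 0.512 + 0.6 × 0.32768 = 0.709. At h = 0.05 the counted value uses p = 0.25: 0.4219 + 0.75 × 0.2373 = 0.600.

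| d | h | DLT-free | Replaced | Counted as DLT |
|---|---|---|---|---|
| 0.20 | 0.02 | 0.709 | 0.700 | 0.665 |
| 0.20 | 0.05 | 0.709 | 0.686 | 0.600 |
| 0.20 | 0.10 | 0.709 | 0.660 | 0.494 |
| 0.10 | 0.05 | 0.906 | 0.897 | 0.814 |
| 0.30 | 0.05 | 0.494 | 0.462 | 0.396 |

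The chance of at least one gap case among six patients, 1 − (1−h)⁶, is 11% at h = 0.02 and 47% at h = 0.10.

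The documents give only a loose ceiling on h. Raised bilirubin is not among the events above 25% in Section 2.3.2. Since 4/15 = 26.7%, at most 3 of 15 patients had it, if all were reported under one term. Two of those were DLT patients with Grade 3 or 4 transaminases, which leaves at most 1/15 = 6.7% (exact 95% upper limit 31.9%). This ceiling covers any grade at any time and requires neither concurrent transaminases, nor relatedness, nor onset in the window. No gap case is documented.

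**The case against.** **The delay criterion may already cover dose 1.** This stands in part. A reader might infer that a patient stopped after dose 1 is simply replaced. The text does not support that as a certainty, because both readings are open.

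**Oversight is strong.** Section 10.1.5 has the SRC review safety data in depth by patient and cohort, and gives related SAEs an ad hoc review. Section 10.6 makes potential drug-induced liver injury an AESI, reportable within 24 hours. Section 6.3.2 already contemplates sequelae "considered related to AST or ALT elevations even if such elevations do not meet the Grade criteria stated above". The SRC will probably see the case, and this lowers the risk. Seeing it does not settle how it is counted, however; declaring a DLT remains optional.

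**Investigator grading could close the gap.** Section 10.4.1.3.2 records the diagnosis in place of the laboratory finding, and Section 10.4.3 leaves grading to the investigator. A confirmed liver injury might be graded 3 or higher. That is possible but not assured.

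**Stopping is not the same as a DLT elsewhere.** Unresolved Grade 2 ALT/AST with normal bilirubin, and a second interruption for a Grade 2 infusion reaction, also stop BNT321 with no DLT instruction. This is correct, so discontinuation alone does not prove an error. Unlike the Hy's law row, though, the ALT/AST row stops BNT321 only if recovery fails or episodes recur.

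**A wider remedy is tempting.** A reader might infer that every possibly related laboratory pattern should be a DLT, that mFOLFIRINOX should be barred as an alternative cause, or that pending work-ups should count. The documents do not support this. Table 8 acts only on a case that meets Hy's law and is judged related, and Section 10.6 requires alternative causes to be excluded before confirmation. mFOLFIRINOX is given throughout the window, and Section 2.3.2 reports raised ALT in 64.0% of patients on it alone.

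**Conclusion.** The gap is real, narrow and minor. It is clear for a related case below Grade 3 after dose 2 that settles within 14 days, and ambiguous after dose 1. A reader might infer that Hy's law cases in general escape the DLT count. They do not: those with Grade 3 or higher transaminases, or with bilirubin of at least 2 × ULN for more than 14 days, are already listed.

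The reach is also limited. Two dose levels are planned, so there is one planned escalation step, to the MTD from the metastatic setting (Section 6.2). Further levels need SRC and health authority approval (Section 4.1.1), and the RP2D is chosen on all available safety, PK and PD data (Section 4.1.5).

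At d = 0.20, gap rates of 2% to 10% would put the written rule's chance of clearing a level about 4 to 21 percentage points above that of a rule counting these cases, if all of them were scored DLT-free. Those rates are assumptions. The 20% pools a metastatic cohort over a dose range not visible in the public copy, and is not a rate for either planned level. The counting conclusion rests only on the Grade 3 cut-offs lying above the Hy's law thresholds.

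**What to change.** - In 6.3.2, add that an event in the DLT assessment period that meets Hy's law under 10.6 and is deemed related to BNT321, so that Table 8 requires permanent discontinuation, is a DLT whatever its grade or duration, after dose 1 or dose 2.
- In the Hy's law row of Table 8, add an instruction to report a DLT under 6.3.2.
- State that the row's no-redose rule takes precedence over the retreatment conditions in 6.3.3, which would otherwise allow a DLT patient back on treatment.

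Leave relatedness, alternative causes (including mFOLFIRINOX) and pending work-ups to the existing 10.6 and SRC process. Sections 4.1.5 and 9.4 and the exemptions for isolated transient elevations need no change.

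The cost is a few lines of protocol wording and a slightly higher observed DLT rate. Occasionally a cohort will be expanded or closed on a case that recovers quickly. That is proportionate for an event the protocol already treats as grounds for never redosing.
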